10.3.2 Intensity of Adverse Events

The intensity of adverse changes in physical signs or symptoms will be graded according to the CTCAE version 4. For all other adverse events not described in the CTCAE, the intensity will be assessed by the Investigator using the following categories:

Mild (Grade 1) – transient or mild discomfort; no limitation in activity; no medical intervention/therapy required.

Moderate (Grade 2) – mild to moderate limitation in activity, some assistance may be needed; no or minimal medical intervention/therapy required.

Severe (Grade 3) – marked limitation in activity, some assistance usually required; medical intervention/therapy required, hospitalization is possible.

Life-threatening (Grade 4) – extreme limitation in activity, significant assistance required; significant medical intervention/therapy required, hospitalization or hospice care probable.

Death (Grade 5) – the event resulted in death.

10.3.3 Action Taken with Study Drug

The action the Investigator took with study drug as a result of the event should be recorded as one of the following:

None – No action was taken with regard to the study drug as a result of the adverse event.

Interrupted – Study drug was stopped due to the adverse event, but was later resumed at the same dose.

Dose decreased – The dose of study drug was decreased as a result of the adverse event.

Permanently discontinued – The subject was withdrawn from the study due to the adverse event.

Only one item should be chosen. If multiple actions apply, the following “worst case” scenario hierarchy should be used to determine the preferred entry:

Discontinued > dose decreased > therapy interrupted.

10.3.4 Definition of Outcome

The outcome of the AE should be recorded as 1 of the following:

Resolved without sequelae – The subject fully recovered from the adverse event with no observable residual effects.

Resolved with sequelae – The subject recovered from the adverse event with observable residual effects.

Not resolved – The adverse event was present at the time of last observation.

Death – The subject died as a result of the adverse event.

10.4 Immediately Reportable Events

10.4.1 Serious Adverse Events

Serious adverse events (SAE) are defined above. The investigator must inform Celgene in writing using a Celgene SAE form or MEDWATCH 3500A form of any SAE within 24 hours of being aware of the event. The written report must be completed and supplied to Celgene by facsimile within 24 hours/1 business day. All SAE's must also be reported to the IRB and DISC in accordance with the institution's policy per 21 CFR 56.

The initial report must be as complete as possible, including an assessment of the causal relationship between the event and the investigational product(s). Information not available at the time of the initial report (*e.g.*, an end date for the adverse event or laboratory values received after the report) must be documented on a follow-up report. A final report to document resolution of the SAE is required. The Celgene tracking number RV-CL-AML-PI-002987 and the institutional protocol number should be included on SAE reports (or on the fax cover letter) sent to Celgene. A copy of the fax transmission confirmation of the SAE report to Celgene should be attached to the SAE and retained with the patient records.

Serious and unexpected AEs that are at least possibly related to the study drug must be reported to the FDA in accordance with 21CFR 312.32 IND Safety Reports.

Celgene Drug Safety Contact Information:

Celgene Corporation

Global Drug Safety and Risk Management

[name]

[name]

[name]

[contact]

E-mail: [contact]

10.4.2 Other Events Requiring Immediate Reporting

Any overdose of lenalidomide should be reported via an SAE form within 24 hours of being made aware of the event, regardless of association with an adverse event. In case the overdose did not result in any adverse event, the Investigator should report this as “overdose, no adverse event” on the SAE form and provide the intended amount, as well as the actual amount, of drug administered. In the event of overdose or exaggerated response, appropriate supportive measures should be employed. At this time, no specific additional measures or unique treatments are known or indicated for management of lenalidomide overdose. Actual treatment should depend on the severity of the clinical situation and the judgment and experience of the treating physician.

10.5 Second Primary Malignancies

Second Primary Malignancies (SPMs) are considered events of interest and should be included as part of the assessment of adverse events throughout the course of the study. Investigators are to report any second primary malignancies as serious adverse events regardless of causal relationship to lenalidomide, occurring at any time for the duration of the study. For all subjects who develop second primary malignancies, sites will be required to submit all diagnostic reports (*e.g.*, pathology, cytogenetics, flow cytometry results) from the indication diagnostic confirmation samples submitted at screening and all reports for the tumor samples from the SPM diagnosis. For SPMs diagnosed at another institution (outside the investigational site), sites are to make every effort to obtain these reports for the SPM confirmation.

10.6 Pregnancies

Pregnancies and suspected pregnancies (including a positive pregnancy test regardless of age or disease state) of a female subject occurring while the subject is on lenalidomide, or within 28 days of the subject’s last dose of lenalidomide, are considered immediately reportable events. Lenalidomide is to be discontinued immediately. The pregnancy, suspected pregnancy, or positive pregnancy test must be reported to Celgene Drug Safety immediately by facsimile or email using the Pregnancy Initial Report Form. The female subject should be referred to an obstetrician-gynecologist, preferably one experienced in reproductive toxicity for further evaluation and counseling.

The Investigator will follow the female subject until completion of the pregnancy, and must notify Celgene Drug Safety immediately about the outcome of the pregnancy (either normal or abnormal outcome) using the Pregnancy Follow-up Report Form. If the outcome of the pregnancy was abnormal (*e.g.*, spontaneous or therapeutic abortion), the Investigator should report the abnormal outcome as an AE. If the abnormal outcome meets any of the serious criteria, it must be reported as an SAE to Celgene Drug Safety immediately by facsimile, or other appropriate method, within 24 hours of the Investigator’s knowledge of the event using the SAE Report Form.

All neonatal deaths that occur within 28 days of birth should be reported, without regard to causality, as SAEs. In addition, any infant death after 28 days that the Investigator suspects is related to the in utero exposure to the IP should also be reported to Celgene Drug Safety immediately by facsimile, or other appropriate method, within 24 hours of the Investigator’s knowledge of the event using the SAE Report Form.

10.6.1 Male Subjects

If a female partner of a male subject taking investigational product becomes pregnant, the male subject taking lenalidomide should notify the Investigator, and the pregnant female partner should be advised to call their healthcare provider immediately.

10.7 Investigator Reporting Responsibilities

The conduct of the study will comply with all FDA safety reporting requirements.

10.7.1 IND Annual Reports

If the FDA has granted an IND number, it is a requirement of 21 CFR 312.33, that an annual report is provided to the FDA within 60-days of the IND anniversary date. 21 CFR 312.33 provides the data elements that are to be submitted in the report. The Annual Report should be filed in the study's Regulatory Binder, and a copy provided to Celgene Corporation as a supporter of this study as follows.

Celgene Corporation
Attn: Medical Affairs Operations
[name]
[name]
[name]

All adverse experience reports must include the patient number, age, sex, weight, severity of reaction (*e.g.*, mild, moderate, severe), relationship to drug (*e.g.*, probably related, unknown relationship, definitely not related), date and time of administration of test medications and all concomitant medications, and medical treatment provided. The investigator is responsible for evaluating all adverse events to determine whether criteria for “serious” and as defined above are present. The investigator is responsible for reporting adverse events to Celgene as described below.

10.7.2 Investigator Reporting to the FDA

Serious adverse events (SAEs) that are **unlisted/unexpected, and at least possibly associated to the drug**, and that have not previously been reported in the Investigators brochure, or reference safety information document should be reported promptly to the Food and Drug Administration (FDA) by telephone or by fax. Fatal or life threatening SAEs that meet the criteria for reporting to the FDA must be reported to the FDA within 7 calendar days after awareness of the event. All other SAEs that meet the criteria for reporting to the FDA must be reported to the FDA within 15 calendar days after awareness of the event. A clear description of the suspected reaction should be provided along with an assessment as to whether the event is drug or disease related.

10.7.3 Adverse event updates/IND safety reports

Celgene shall notify the Investigator via an IND Safety Report of the following information:

- Any AE associated with the use of drug in this study or in other studies that is both serious and unexpected.
- Any finding from tests in laboratory animals that suggests a significant risk for human subjects including reports of mutagenicity, teratogenicity, or carcinogenicity.

The Investigator shall notify his/her IRB/EC promptly of these new serious and unexpected AE(s) or significant risks to subjects.

The Investigator must keep copies of all AE information, including correspondence with Celgene and the IRB/EC, on file (see Section 15.6 for records retention information).

11. DISCONTINUATIONS

11.1 Discontinuation of Subjects

A subject must be discontinued from protocol-prescribed therapy under the following circumstances:

- Consent withdrawal at the subject's own request or at the request of their legally authorized representative;
- Unacceptable toxicity or adverse event as determined by the Principal Investigator and/or subject;
- Significant deviation from inclusion/exclusion criteria, in the opinion of the Principal Investigator;
- If, in the Principal Investigator's opinion, continuation in the study could be detrimental to the subject's well-being;
- Relapsed or progressive disease;
- Initiation of chemotherapy for relapsed or progressive disease.

If a female subject or the female partner of a male subject who is required to use defined contraceptive methods becomes pregnant after the study, the female subject or pregnant partner must be followed until the outcome of the pregnancy is known.

As far as possible, all end-of-study examinations must be performed on all subjects who receive the study drug but do not complete the study according to protocol. All subjects who discontinue from protocol-prescribed therapy for any of the reasons above will be followed for a period of 30 days following the last day of study drug administration.

11.2 Replacement of Subjects

Subjects who are withdrawn prior to completion of 21 days of lenalidomide for any reason will be replaced.

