
Study Design:
	
This is an open-label, phase I dose escalation study of lenalidomide after allo-HCT in AML and MDS subjects with MRD detected by the CD34+ mixed chimerism analysis. The study is designed to evaluate the safety profile, MTD and biologic activity of lenalidomide after allo-HCT in patients with AML and MDS
 
The dose levels of lenalidomide will be as follows:
 
Dose Level 1: 2.5 mg PO QOD Day 1-21 for 28 day cycle X 2 cycles Dose Level 2: 2.5 mg PO QD Day 1-21 for 28 day cycle X 2 cycles Dose Level 3: 5 mg PO QD Day 1-21 for 28 day cycle X 2 cycles Dose Level 4: 7.5 mg PO QD Day 1-21 for 28 day cycle X 2 cycles
 
Subjects will be enrolled in cohorts of three (3). Lenalidomide will be administered for 21 consecutive days in a 28 day cycle X 2 cycles. The starting dose will be 2.5 mg given orally every other day for 21 days.

Subjects will be individually assessed for safety and dose limiting toxicity (DLT) for the purpose of determining the MTD .Three eligible subjects will be enrolled in sequential cohorts at increasing dose levels until at least one DLT is seen between the first dose and 14 days after the last dose of lenalidomide. For this study, MTD will be defined as the highest dose which no more than 34% of the subjects observed at a given dose level experience a DLT. The following dose escalation rules will be used and applied:

1. Three subjects are initially studied at each dose level.
2. If none of these 3 subjects experience DLT, then the dose is escalated to the next dose level in 3 subsequent subjects.
3. If 1 of these 3 subjects experiences DLT at current dose, then up to 3 more subjects are accrued at the same level.
 - a) If none of these 3 additional subjects experience DLT, then the dose is escalated to the next dose level in 3 subsequent subjects.
 - b) If 1 or more of these 3 additional subjects experiences DLT, then the MTD is considered to have been exceeded and the previous dose level will be the MTD.
4. If 2 or more of the initial 3 subjects at a dose level experience DLT, then the MTD is considered to have been exceeded and dose escalation will be stopped. Up to 3 more subjects are treated at the next lower dose.

A subject must meet one of the following 3 criteria to be evaluable for subsequent dose-escalation decisions:

1. Complete at least 21 days of lenalidomide without a DLT by 14 days after the last dose of lenalidomide;

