2. Experienced a DLT between the first dose and 14 days after the last dose of lenalidomide; or
3. Withdrawn from the study after at least 14 days of lenalidomide administration.

If a subject does not meet any of these criteria, the subject is not evaluable for dose escalation decisions and will be replaced in that cohort. No more than 3 subjects will be added simultaneously to a dose cohort during dose escalation.

The study ends when there is a maximum dose where 2 or more subjects out of 6 have a DLT, or when the maximum sample size of twenty four (24) subjects has been reached.

Dose Limiting Toxicity

DLT will be defined as any of the following adverse events that are not clearly unrelated to drug administration or treatment-emergent from lenalidomide and constitute a change from baseline irrespective of outcome. For the purpose of dose-escalation decisions and MTD

	
determination, only DLTs that occur within 14 days after the last dose of lenalidomide administration will be taken into account.
 
 1. Grade 3 or greater nausea, diarrhea, or vomiting despite the use of maximal medical intervention; 2. Grade 3 or greater acute GVHD despite the use of maximal medical intervention; 3. Any other clinically significant non-hematologic toxicity of grade 3 or greater considered not related to the underlying disease or intercurrent illness; 4. Grade 3 or greater neutropenia; 5. Grade 4 thrombocytopenia or platelet count ≤ 50 thou/mm³ by day 28 of lenalidomide administration; or 6. Any treatment-related effect leading to a subject missing 3 or more doses of lenalidomide. 
Correlative Studies:
 
Peripheral blood will be collected to examine the CD34+ specific chimerism.

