4.2 Dose Escalation

The dose levels of lenalidomide will be as follows:

- Dose Level 1: 2.5 mg PO QOD Day 1-21 for 28-day cycle X 2 cycles
- Dose Level 2: 2.5 mg PO QD Day 1-21 for 28-day cycle X 2 cycles
- Dose Level 3: 5 mg PO QD Day 1-21 for 28-day cycle X 2 cycles
- Dose Level 4: 7.5 mg PO QD Day 1-21 for 28-day cycle X 2 cycles

The dose escalation phase of the study will utilize a standard “3 + 3” design to estimate the MTD for lenalidomide. A description of the statistical characteristics (probabilities of halting or continuing dose escalation) of this design is provided in Appendix G: Statistical Characteristics of the “3+3” Design. For this study, MTD will be defined as the highest dose at which no more than 34% of the subjects observed at a given dose level experience a DLT. Subjects will be individually assessed for safety and DLTs for the purpose of determining the MTD. Three eligible subjects will be enrolled in sequential cohorts at increasing dose levels until at least one (1) DLT is seen between the first dose and 14 days after the last dose of lenalidomide. The following dose escalation rules will be used and applied:

1. Three subjects are initially studied at each dose level.
2. If none of these 3 subjects experience DLT, then the dose is escalated to the next dose level in 3 subsequent subjects.
3. If 1 of these 3 subjects experiences DLT at the current dose, then up to 3 more subjects are recruited at the same dose level.
 - a) If none of these 3 additional subjects experience DLT, then the dose is escalated to the next dose level in 3 subsequent subjects.
 - b) If 1 or more of these 3 additional subjects experiences DLT, then the MTD is considered to have been exceeded and the previous dose level will be the MTD.
4. If 2 or more of the initial 3 subjects at a dose level experience DLT, then the MTD is considered to have been exceeded and dose escalation will be stopped. Up to 3 more subjects are treated at the next lower dose.

A subject must meet one of the following 3 criteria to be evaluable for dose-escalation decisions:

[figure not shown]
1. Completed at least 21 days of lenalidomide without a DLT by 14 days after the last dose of lenalidomide;

2. Experienced a DLT between the first dose and 14 days after the last dose of lenalidomide; or
3. Withdrawn from the study after at least 14 days of lenalidomide administration.

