13.2.2 Dose Limiting Toxicity Evaluable Population

A subject is evaluable in dose-escalation decisions provided the subject has received at least five doses without a DLT, has experienced a DLT, or has been withdrawn from the study prior to completing of 21 days of lenalidomide due to a DLT. If a subject withdraws from the study without meeting these criteria, the subject will be replaced in that cohort. Tabulations of DLTs will only include the DLT-evaluable population.

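### The synopsis and section 4.2, section 11.2 and section 13.2.2 give incompatible rules for who counts in dose-escalation decisions and who is replaced, and none is said to govern

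*Combined protocol and SAP*

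**What the plan says.** Three rules cover the same subjects.

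- **Synopsis (Study Design) and section 4.2.** A subject counts on meeting any one of three criteria. The first is "Completed at least 21 days of lenalidomide without a DLT by 14 days after the last dose of lenalidomide". The second is "Experienced a DLT between the first dose and 14 days after the last dose of lenalidomide". The third is withdrawal after at least 14 days of drug. Only the synopsis adds the consequence of meeting none of them: "the subject is not evaluable for dose escalation decisions and will be replaced in that cohort". Section 4.2, as supplied, lists the criteria without a replacement sentence.
- **Section 11.2.** "Subjects who are withdrawn prior to completion of 21 days of lenalidomide for any reason will be replaced". It makes no exception for a DLT or for 14 to 20 days of drug.
- **Section 13.2.2.** A subject counts "provided the subject has received at least five doses without a DLT", or with a DLT, or if the subject "has been withdrawn from the study prior to completing of 21 days of lenalidomide due to a DLT". Then: "If a subject withdraws from the study without meeting these criteria, the subject will be replaced in that cohort".

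Sections 4.2 and 13.2.2 both say that they define who is evaluable for dose-escalation decisions, so 13.2.2 is not only a population for tabulation. Nothing in the text cross-refers between the rules or gives an order of precedence.

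**The concern.** The number of DLTs among evaluable subjects at a level drives every escalation decision and the maximum tolerated dose (MTD), which is the primary objective. If a subject's status depends on the section consulted, two teams that both follow the protocol can act differently on identical data.

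The five-dose clause is the permissive one. Compared with 4.2, it puts DLT-free subjects with little observation into the denominator, and this favours escalation. Section 11.2 raises a different problem. It replaces some subjects whom the other sections count and does not say whether they stay in the count. If they do, a cohort can exceed the 3 or 6 subjects that the escalation rules and section 13.1 provide for. The Appendix G probabilities assume one fixed denominator rule, so they describe the trial only once that rule is settled.

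**Working it through.** **1. The rules applied to the same subject.** The fifth dose falls on day 5 with daily dosing and on day 9 with every-other-day dosing.

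| Subject | Synopsis / 4.2 | 11.2 | 13.2.2 |
|---|---|---|---|
| No DLT, fewer than five doses, withdrawn before day 14 | not evaluable, replaced | replaced | not evaluable, replaced |
| No DLT, at least five doses, withdrawn before day 14 | not evaluable, replaced | replaced | evaluable, kept |
| No DLT, withdrawn on days 14–20 | evaluable, kept | replaced | evaluable, kept |
| DLT, withdrawn before day 21 | evaluable, kept | replaced | evaluable, kept |
| No DLT, 21 or more days of drug | evaluable, kept | kept | evaluable, kept |

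The rules disagree in the three middle rows. There is a rare reverse case in the third row. An every-other-day subject withdrawn near day 14 has 7 scheduled doses; one who missed three or more of them for unrelated reasons meets the 14-day criterion of 4.2 but not the five-dose one.

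**2. Appendix G reproduced.** With true DLT rate p and q = 1 − p,

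P(escalate) = q³ + 3pq² × q³.

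At p = 0.20, 0.33, 0.40, 0.50 this gives 0.709, 0.434, 0.309, 0.172. Appendix G prints 0.71, 0.43, 0.31, 0.17.

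**3. One cohort, no early-stopping share assumed.** Two subjects complete without DLT; the third stops DLT-free after five daily doses.

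- Under 13.2.2: 0 of 3, so escalation is certain.
- Under the synopsis and 11.2: the third subject is replaced. If the replacement has no DLT (probability q), the dose is escalated. If the replacement has a DLT (probability p), three more subjects must all be DLT-free. P(escalate) = q + p × q³ = 0.902, 0.769, 0.686, 0.563 at the same four rates. At p = 0.40: 0.60 + 0.40 × 0.216 = 0.686.

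**4. Averaged over cohorts, with assumed shares.** The documents give no early-stopping share. Assume that a share s of subjects stops after five daily doses and that the DLT hazard is constant over a window of W days. Two cycles plus 14 days give W = 28 + 21 + 14 = 63. Because section 4.2 describes Figure 4 as showing MTD determination in Cycle 1, W = 21 + 14 = 35 is shown as well.

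- Risk of an early stopper, observed for 5 + 14 = 19 days: pe = 1 − (1 − p)^(19/W). At p = 0.40 this is 0.143 (W = 63) or 0.242 (W = 35).
- Counted rate under 13.2.2: (1 − s)p + s·pe.
- Counted rate under the synopsis/4.2 rule (DLT-free stoppers replaced): [(1 − s)p + s·pe] / [(1 − s) + s·pe].

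Putting each counted rate into the formula of step 2 gives P(escalate) for s = 5/10/20%:

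| p | W | Appendix G | 13.2.2 | Synopsis / 4.2 |
|---|---|---|---|---|
| 0.20 | 63 | 0.71 | 0.723 / 0.738 / 0.766 | 0.703 / 0.696 / 0.681 |
| 0.33 | 63 | 0.43 | 0.456 / 0.477 / 0.522 | 0.427 / 0.418 / 0.399 |
| 0.40 | 63 | 0.31 | 0.331 / 0.353 / 0.399 | 0.302 / 0.294 / 0.277 |
| 0.40 | 35 | 0.31 | 0.322 / 0.336 / 0.363 | 0.297 / 0.284 / 0.257 |
| 0.50 | 63 | 0.17 | 0.190 / 0.209 / 0.252 | 0.166 / 0.161 / 0.148 |

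**5. Section 11.2, with DLT subjects counted and also replaced.** Let f be the share of DLT subjects withdrawn before day 21. Assume no DLT-free withdrawals, and treat one DLT among four like one among three, since the protocol has no rule for four. Then

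P(escalate) = q³ + [3p(1 − f)q² + 3pf·q³] × q³.

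At p = 0.40 and f = 25/50/75/100% this is 0.300/0.291/0.281/0.272, against 0.309 without the extra subjects. A reading of 11.2 that drops these DLTs would raise the probability, but it contradicts the second criterion of 4.2 and section 13.2.2, so no figure is given for it.

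**The case against.** The strongest reply accepts the conflict between five doses and 14 or 21 days but limits its reach.

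- *Section 11.2 concerns replacement, not counting.* Sections 4.2 and 13.2.2 agree that a subject with a DLT counts, so the DLT itself need not be lost. This stands. What remains for that subject is whether an extra subject is added, and step 5 shows a small effect towards less escalation. The protocol still has no rule for the resulting cohort size, and both the synopsis and 13.2.2 tie replacement to not being evaluable.
- *Section 4.2 also admits partly observed subjects*, at 14 or 21 days out of two planned 21-day courses. True. The model in step 4 gives all subjects other than the early stoppers the full risk, and it puts every early stop at the earliest evaluable point. Spreading stops evenly over days 5–13 at p = 0.40 gives 0.328/0.348/0.389 (W = 63) or 0.319/0.328/0.348 (W = 35), slightly less than the table shows.
- *The shares are invented, and at 5% the shift from Appendix G is only about 0.01 to 0.02.* Also true. DLT item 6 in section 4.3 turns many treatment-related early stops into DLTs. On the other hand, section 11.1 requires discontinuation for relapse, consent withdrawal or investigator judgement, so DLT-free early stops are foreseeable here.
- *The trial is descriptive.* Its escalation rule is nevertheless a decision rule and has to give one answer for one set of data.

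**Conclusion.** The concern holds and should be fixed before the escalation rule is applied. The decisive conflict is the five-dose threshold in 13.2.2 against the 14- and 21-day criteria in the synopsis and 4.2. Section 11.2 adds a further conflict for DLT-free withdrawals on days 14–20, and leaves the cohort size undefined when a subject withdrawn with a DLT is replaced.

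For a cohort with one disputed subject, the choice of rule moves the probability of escalation from certainty to between 0.90 and 0.56 over true DLT rates of 0.20 to 0.50. That figure is conditional on such a subject occurring. The averaged shifts rest on assumed stopping shares, a constant hazard and the chosen window, and they are modest at low shares. The severity rests on the contradictory decision rule for the primary objective, not on those averages.

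**What to change.** Reconcile the passages into one evaluability and replacement rule and use it word for word in the synopsis, 4.2, 11.2 and 13.2.2:

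1. State that a subject with a DLT in the window always stays in the DLT count, as 4.2 and 13.2.2 already agree.
2. Limit 11.2 to subjects who are not evaluable under that rule.
3. Set one minimum-exposure criterion for DLT-free subjects in place of the five-dose, 14-day and 21-day thresholds. The sponsor chooses which.

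In the same amendment, it would help to say what the cap of 24 counts. Section 13.1 refers both to enrolled and to evaluated subjects, section 5.1 to subjects who receive lenalidomide, and section 4.4 removes subjects untreated if chimerism stays above 90%. This is a side point; the main concern does not depend on it.

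The cost is a wording amendment and possibly a few more replacements than under 13.2.2. Four levels of six subjects already make 24, so the basis of the cap decides whether replacements fit within it.

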6.2 Instructions for initiation of lenalidomide

Lenalidomide may begin if each of the following criteria are met:

- The ANC is ≥ 1.0 thou/mm³;
- The platelet count is ≥ 50 thou/mm³;
- The CD34+ donor chimerism is $\leq 90\%$ at day +60 or +120 (± 7 days) post-transplant.

Lenalidomide dosing will continue as scheduled unless a DLT occurs.

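### Section 11.2 replaces every subject withdrawn before 21 days, with no exception for a DLT, which contradicts the Synopsis and Section 13.2.2 and can create cohorts that the 3+3 rules do not cover

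*Combined protocol and SAP*

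**What the plan says.** Three parts of the protocol deal with replacement.

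- **Section 11.2 (Replacement of Subjects):** "Subjects who are withdrawn prior to completion of 21 days of lenalidomide for any reason will be replaced". There is no exception for a DLT.
- **Synopsis, Study Design:** a subject who meets none of three criteria is replaced, in these words: "the subject is not evaluable for dose escalation decisions and will be replaced in that cohort". Having had a DLT in the window is one of the three criteria.
- **Section 13.2.2 (DLT evaluable population):** among the evaluable it names a subject who "has been withdrawn from the study prior to completing of 21 days of lenalidomide due to a DLT". It then limits replacement: "If a subject withdraws from the study without meeting these criteria, the subject will be replaced in that cohort".

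Section 4.2 gives the same evaluability criteria as the Synopsis, including criterion 2: "Experienced a DLT between the first dose and 14 days after the last dose of lenalidomide; or". It does not repeat the Synopsis sentence on replacement.

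Two further passages show how a DLT can lead to withdrawal. Section 6.2 says: "Lenalidomide dosing will continue as scheduled unless a DLT occurs". Section 10.3.3 defines permanent discontinuation for an adverse event as: "The subject was withdrawn from the study due to the adverse event".

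**The concern.** The MTD is the primary objective and rests on DLT counts in cohorts of 3 or 6. One subject's status can change the decision: 0 of 3 escalates, 1 of 3 expands the cohort. A subject with a DLT who is withdrawn before 21 days must be replaced under 11.2 and must not be replaced under the Synopsis and 13.2.2. Nothing says which prevails.

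Following 11.2 literally leaves two ways to proceed.

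- **Count the DLT and enrol a replacement.** The initial cohort becomes 4 or more, or the expanded cohort 7 or more. Sections 4.2 and 11.3 are written for 3 initial subjects, 3 additional subjects and 2 or more DLTs out of 6. They do not say whether a DLT in a replacement counts as a second DLT among the initial three, or what 2 of 7 (29%) or 2 of 8 (25%) means.
- **Treat the replaced subject as no longer counting.** The early DLT is then lost from the primary endpoint.

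The first way also exposes extra subjects at a level that has just produced a DLT. It strains the cap as well: four levels of six already make 24, and Section 13.1 speaks of subjects both as enrolled and as evaluated when it sets that limit.

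**Working it through.** **Inputs.** The 3+3 rules are from Section 4.2 and the operating characteristics from Appendix G. Let p be the true DLT probability and c = 1 − p. Let f be the share of DLTs that occur before 21 days and end in withdrawal. The documents do not give f, so 25%, 50% and 75% are assumed.

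**Step 1: the plan's own figure.** P(escalate) = c³ + 3pc²·c³ = c³ + 3pc⁵.

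- p = 0.33: 0.3008 + 0.1337 = 0.434. Appendix G gives 0.43.
- p = 0.40: 0.2160 + 0.0933 = 0.309. Appendix G gives 0.31.

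The other eight columns also agree to two decimals.

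**Step 2: how often 11.2 is triggered.** At least one of the first three subjects has an early DLT with withdrawal with probability 1 − (1 − pf)³. At p = 0.33:

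- f = 25%: 1 − 0.9175³ = 0.23
- f = 50%: 1 − 0.835³ = 0.42
- f = 75%: 1 − 0.7525³ = 0.57

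This is 11.2 applied literally. Where enrolment stops at a second DLT, some of these replacements would not be made.

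**Step 3: DLT counted and a replacement enrolled.** Escalation needs no DLT at all, or exactly one DLT in the first stage and none in the second. One DLT in the first stage arises in two ways:

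- a subject who is not replaced has it: 3·p(1 − f)·c²
- a replaced subject has it and all three remaining subjects are free of DLT: 3·pf·c³

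Their sum is 3pc²(1 − pf), so P(escalate) = c³ + 3pc⁵(1 − pf). At p = 0.33:

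- f = 25%: 0.3008 + 0.1337 × 0.9175 = 0.42
- f = 50%: 0.3008 + 0.1337 × 0.835 = 0.41
- f = 75%: 0.3008 + 0.1337 × 0.7525 = 0.40

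Simulation of the same rule agrees to within rounding.

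**Step 4: DLT lost with the replaced subject.** The DLT probability among counted subjects becomes q = p(1 − f)/(1 − pf), which goes into the Step 1 formula. At p = 0.33, q = 0.270, 0.198, 0.110.

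| | f = 25% | f = 50% | f = 75% |
|---|---|---|---|
| **p = 0.33 (Appendix G: 0.43)** | | | |
| Replacement triggered, initial cohort | 0.23 | 0.42 | 0.57 |
| P(escalate), DLT counted and replaced | 0.42 | 0.41 | 0.40 |
| P(escalate), DLT lost | 0.56 | 0.71 | 0.89 |
| **p = 0.40 (Appendix G: 0.31)** | | | |
| P(escalate), DLT counted and replaced | 0.30 | 0.29 | 0.28 |
| P(escalate), DLT lost | 0.43 | 0.60 | 0.83 |

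**Smaller f.** At p = 0.33 and f = 10%, a replacement is triggered with probability 1 − 0.967³ = 0.10. Escalation is 0.3008 + 0.1337 × 0.967 = 0.43 if the DLT is counted and 0.48 if it is lost.

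**The case against.** A reader might infer from 11.2 that the primary DLT count loses the subjects with early toxicity, so that escalation becomes too easy. The documents do not support that as the plan's effect. Section 11.2 speaks only of replacement, not of evaluability or tabulation. The Synopsis and Section 4.2 make a subject with a DLT evaluable, and 13.2.2 names the exact case. Section 11.3 counts DLTs in a dose cohort without any exclusion. On the count, the texts agree. They conflict on whether another subject is enrolled. With the DLT counted, escalation moves slightly down, not up.

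The path from DLT to withdrawal is also looser than it first looks. Section 6.2 does not say that a subject with a DLT leaves the study. Section 10.3.3 is a coding list that also allows interruption and dose decrease. Section 11.1 leaves discontinuation for toxicity to the judgement of the principal investigator and/or the subject. The DLT window runs over two cycles plus 14 days after the last dose, so many DLTs may fall outside the reach of 11.2, and nothing in the documents supports f = 75% in particular.

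All of this stands, and it limits the size of the problem. It does not remove the contradiction. Section 11.2 is the section that staff will consult on replacement, and it is unqualified. In the body of the protocol only 13.2.2 limits replacement, because Section 4.2 lacks the Synopsis sentence. Elsewhere in the protocol replacement applies only to subjects who are not evaluable, so someone could mistakenly carry that meaning over to 11.2.

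**Conclusion.** The point holds as an internal contradiction that bears on the primary endpoint. Section 11.2 requires replacement of a subject withdrawn early for a DLT, and the Synopsis and 13.2.2 do not allow it.

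Under the better-supported reading, the DLT counts and an extra subject is enrolled. The effect on escalation is small: at p = 0.33, from 0.43 to 0.40 at most over the assumed range of f. The main harm is undefined decision rules for cohorts above 3 or 6, possibly in a sizeable share of initial cohorts (0.23 to 0.57 for f from 25% to 75%, and 0.10 at f = 10%), together with added exposure at a level with a known DLT. Appendix G no longer describes such a design.

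The rise in escalation to 0.56, 0.71 or 0.89 would need staff to drop the early DLT, against the Synopsis, 4.2 and 13.2.2. It shows what a misreading could cost and is not the expected effect. Every figure beyond Appendix G depends on the assumed f.

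**What to change.** Amend Section 11.2 to state that only subjects who are not DLT-evaluable are replaced. It should add that a subject who has had a DLT in the window stays in the cohort count, whatever the number of days or doses received, and is not replaced. Remove the clause that extends replacement to every reason for withdrawal. Have the Synopsis, 4.2, 11.2 and 13.2.2 all refer to one evaluability definition.

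The cost is one sentence in a protocol amendment. It adds no subjects, avoids unneeded replacements, and brings the DLT count back to the rules that Appendix G describes. It changes counting only, not the management of any subject.

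Separately, the sponsor must reconcile the minimum exposure for subjects without a DLT. The Synopsis and 4.2 use 21 days, or withdrawal after at least 14 days. Section 13.2.2 uses five doses. Section 11.2 replaces anyone withdrawn before 21 days. The sentence proposed here does not settle that.
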